10.1.6.1 Data Collection Instruments

Curebase will provide eCRFs to each subject who signs an informed consent and completes the clinic visit screening. These forms are used to transmit the information collected in the performance of this study to sponsor and regulatory authorities. After completion of the entry process, computer logic checks will be run to identify items, such as inconsistent dates, missing data, and questionable values. Queries may be issued by the PI or designees and will be addressed by the clinic research staff. The PI must review the eCRFs for completeness and accuracy and must e-sign the appropriate eCRFs as indicated. Furthermore, the investigator must retain full responsibility for the accuracy and authenticity of all data entered on the eCRFs. The completed eCRFs are the sole property of the sponsor and should not be made available in form to third parties, except for authorized representatives of appropriate governmental regulatory authorities.

Investigators and their representatives will be required to complete a training on using the Curebase platform prior to working with subjects, including how to enter data correctly, how to enter protocol deviations and AEs, and how to correct mistakes. Trainings will be tracked by Curebase on study-specific activation logs. Following written SOPs, the study monitors will verify that the clinical study is conducted and data are generated, documented, and reported in compliance with the protocol, ICH GCP, and applicable regulatory requirements.

Study personnel at each research clinic will enter data corresponding to a subject's visit into the protocol-specific eCRF. If a correction is required for an eCRF, the time and date stamps track the person entering or updating eCRF data and creates an electronic audit trail. The Investigator is responsible for all information collected on subjects enrolled in this study. All data collected during the course of this study must be reviewed and verified for completeness and accuracy by the Investigator.

10.1.6.2 Data Management Procedures

All data will be entered into Curebase, which is a validated database. The Curebase team or delegate will be responsible for data processing, in accordance with procedural documentation. Database lock will occur once quality assurance procedures have been completed. All procedures for the handling and analysis of data will be conducted using good computing practices meeting FDA guidelines for the handling and analysis of data for clinical trials.

10.1.6.3 Data Quality Control and Reporting

Quality control (QC) procedures will be implemented beginning with the data entry system. After the data has been entered into the Curebase database, a system of computerized data validation checks will be implemented and applied to the database every 2 weeks. Query reports pertaining to missing data or data discrepancies will be forwarded to the Investigators, clinical team and study monitors for clarification/resolution. A Curebase representative will follow up to ensure that the corrections are completed and documented appropriately. The study database will be updated in accordance with the resolved queries. Following completion of the study data collection, Curebase will provide a thorough quality control review of all records. Finalized data will then be designated for database lock prior to statistical analysis. In addition, following written standard operating procedures (SOPs), the monitor will verify that the clinical study is conducted and data are generated, documented (recorded), and reported in compliance with the protocol, ICH GCP and applicable regulatory requirements.

The investigators will provide direct access to all study related records, source data/documents, and reports for the purpose of monitoring and auditing by the sponsor, and inspection by the relevant regulatory authorities.

10.1.6.4 Archival of Data and Record Retention

The database is safeguarded against unauthorized access by established security procedures. Appropriate backup copies of the database and related software files will be maintained. Databases are backed up by the Curebase database administrator in conjunction with any updates or changes to the database.

At critical junctures of the protocol (e.g., production of interim reports and final reports), data for analysis are locked and cleaned per established procedures.

All data pertaining to a clinical study, including protected health information (PHI), will be retained for the duration of the study, and for 2 years thereafter, in compliance with International Conference on Harmonisation (ICH) E6 Section 4.9.5 and specified in ICH E6 (Section 8) until at least 2 years after the last approval of a marketing application for a specified treatment being investigated or, if an application is not approved, until at least 2 years after the investigation is discontinued and regulatory authorities are notified. In addition, ICH E6 Section 4.9.5 states that the study records should be retained until an amount of time specified by applicable regulatory requirements or for a time specified in the agreement between the investigator and sponsor. At this point, the identifiable PHI obtained during the study will be deleted. Curebase will share pseudonymized data collected from subjects with metaMe Health Inc.

After 2 years have elapsed since the completion of a clinical investigation, Curebase will retain a de-identified version of the data obtained during that study. Curebase may retain these data indefinitely and may use them for a variety of purposes that will include, but are not be limited

to, making improvements to the Curebase product. MetaMe Health will be permitted to retain the pseudonymized Curebase data set, even after the 2-year post-study period has elapsed.

Curebase will not delete clinical data, even upon request, during the clinical study and for 2 years thereafter. Although Curebase respects the rights of its users to be forgotten, Curebase is also bound by an obligation to deliver study data to the Sponsor for scientific analysis, and to fulfill monitoring obligations.

MetaMe Health reserves the right to keep the pseudonymized data retrieved from Curebase for the entire duration the company is functioning and active. MetaMe Health will keep this information in a private and secure internal database.

10.1.6.5 Monitoring

Electronic monitoring visits will be conducted by representatives of Curebase, Inc according to the U.S. CFR Title 21 Parts 50, 56, and 312 and ICH Guidelines for GCP (E6). Study investigators will provide direct access to all clinical records, study source data/documents, and reports for the purpose of monitoring and auditing by the sponsor, and inspection by local and regulatory authorities. By signing this protocol, the Investigator grants permission to Curebase and appropriate regulatory authorities to conduct monitoring and/or auditing of all appropriate study documentation.

10.1.6.6 Protocol Deviations

A protocol deviation is any noncompliance with the clinical study protocol and ICH GCP requirements. The noncompliance may be either on the part of the subject, the investigator, or the study research staff. As a result of deviations, corrective actions are to be developed by the study physicians and implemented promptly.

These practices are consistent with ICH GCP:

- 4.5 Compliance with Protocol, sections 4.5.1, 4.5.2, and 4.5.3
- 5.1 Quality Assurance and Quality Control, section 5.1.1
- 5.20 Noncompliance, sections 5.20.1, and 5.20.2.

It is the responsibility of the study physicians and study monitors to use continuous vigilance to identify and report deviations within 10 working days of identification of the protocol deviation, or within 10 working days of the scheduled protocol-required activity. All deviations must be categorized as either significant or minor. Significant deviations are those events that cause or could cause harm to subjects or others or that affect the fidelity of the research. Curebase will maintain a database of protocol deviations for the duration of the study and shall be responsible for triaging report writing and internal documentation. Significant protocol deviations will be

sent to the reviewing Institutional Review Board (IRB) per their policies. The study physicians and study monitors are responsible for knowing and adhering to the reviewing IRB requirements.

10.1.6.7 Clinical Trial Results Disclosure

metaMe will post the results of clinical trials on ClinicalTrials.gov and/or other publicly accessible websites, as required by metaMe policy/standard, applicable laws, and/or regulations.

10.1.6.8 Publication and Data Sharing Policy

Curebase will provide metaMe with all data collected during the study. After study completion, only metaMe may make study information available to other study investigators or to regulatory agencies, except as required by law or regulation. Except as otherwise allowable in the clinic research agreement, any public disclosure (including publicly accessible websites) related to the protocol or study results, other than study recruitment materials and/or advertisements, is the sole responsibility of the sponsor. metaMe reserves the right to publish any data from the study without the consent of investigators. Manuscript authorship for any peer-reviewed publication will appropriately reflect contributions to the production and review of the document.

APPENDIX A ROME IV CRITERIA

Question	Answer
1. In the last 3 months, how often did you have pain anywhere in your abdomen?	0. Never (Skip to end of questionnaire) 1. Less than one day a month 2. One day a month 3. Two to three days a month 4. Once a week 5. Two to three days a week 6. Most days 7. Every day 8. Multiple times per day or all the time
2. How often did this pain in your abdomen happen close in time to a bowel movement -- just before, during, or soon after? (Percent of times with pain)	0. %0 or Never 1. 10% 2. 20% 3. 30% 4. 40% 5. 50% 6. 60% 7. 70% 8. 80% 9. 90% 10. 100%
3. How often did your stools become either softer than usual or harder than usual when you had this pain? (Percent of times with pain)	0. %0 or Never 1. 10% 2. 20% 3. 30% 4. 40% 5. 50% 6. 60% 7. 70% 8. 80% 9. 90% 10. 100%
4. How often did your stools become either more frequent than usual or less frequent than usual when you had this	0. %0 or Never 1. 10% 2. 20% 3. 30% 4. 40% 5. 50%

pain? (Percent of times with pain)	6. 60% 7. 70% 8. 80% 9. 90% 10. 100%
5. Has it been 6 months or longer since you started having this pain?	0. No 1. Yes

Rome IV Scoring

Irritable Bowel Syndrome

Must fulfill the following criteria for the past 3 months:

1. Recurrent abdominal pain

Q1 = at least weekly

2. Pain is associated with two or more of the following criteria:

a. Related to defecation

Q2 = at least 30% of occasions

b. Associated with a change in frequency of stool

Q3 = at least 30% of occasions

c. Associated with a change in form (appearance) of stool

Q4 = at least 30% of occasions

1. Symptom onset at least 6 months prior to diagnosis

Q5 = yes

APPENDIX B GUT-DIRECTED HYPNOTHERAPY SESSION SCRIPTS

IBS Session One

Term	Percentage
Climate change	95
Global warming	100
Green energy	98
Carbon footprint	92
Sustainable development	90
Renewable energy	88
Emissions reduction	85
Green economy	80
Carbon tax	78
Carbon pricing	98

Page 73 of 132

A horizontal bar chart illustrating the percentage of the population aged 65+ in 2010 across 20 countries. The x-axis represents the percentage of the population aged 65+, ranging from 0% to 30%. The y-axis lists the countries. The bars are black and show the following approximate values:

[figure not shown]
Country	Percentage (approx.)
Argentina	20.5%
Australia	21.5%
Austria	22.5%
Belgium	23.5%
Brazil	24.5%
Canada	25.5%
Chile	26.5%
Costa Rica	27.5%
Czech Republic	28.5%
Denmark	29.5%
Finland	30.5%
France	31.5%
Germany	32.5%
Greece	33.5%
Hungary	34.5%
Italy	35.5%
Japan	36.5%
Mexico	37.5%
Netherlands	38.5%
Norway	39.5%
Portugal	40.5%
Spain	41.5%
Sweden	42.5%
Switzerland	43.5%
Turkey	44.5%
United Kingdom	45.5%
United States	46.5%

Page 74 of 132

[figure not shown]
Confidential

Page 75 of 132

Page 77 of 132

[figure not shown]

[figure not shown]
IBS Session Two

[figure not shown]
A 10x10 grid of black bars representing data points. The bars are arranged in a grid pattern, with some bars being significantly longer than others, indicating varying data values. The bars are black and set against a white background.

Page 79 of 132

[figure not shown]
IBS Session Three

[figure not shown]
Index	Length
1	100
2	100
3	100
4	100
5	100
6	100
7	100
8	100
9	100
10	100
11	100
12	100
13	100
14	100
15	100
16	100
17	100
18	100
19	100
20	100

Page 83 of 132

Confidential

[figure not shown]
IBS Session Four

Page 85 of 132

A bar chart illustrating the percentage of the population aged 65 and older in 2010 across various entities. The x-axis represents the percentage, ranging from 0% to 20% in increments of 2%. The y-axis lists the entities. The bars are black and show the following approximate values:

Entity	Percentage (%)
Alabama	16.5
Alaska	15.5
Arizona	15.5
Arkansas	15.5
California	15.5
Colorado	15.5
Connecticut	15.5
District of Columbia	15.5
Florida	15.5
Georgia	15.5
Hawaii	15.5
Idaho	15.5
Illinois	15.5
Indiana	15.5
Iowa	15.5
Kansas	15.5
Kentucky	15.5
Louisiana	15.5
Maine	15.5
Maryland	15.5
Massachusetts	15.5
Michigan	15.5
Minnesota	15.5
Mississippi	15.5
Missouri	15.5
Montana	15.5
Nebraska	15.5
Nebraska	15.5
North Carolina	15.5
North Dakota	15.5
Ohio	15.5
Oklahoma	15.5
Oregon	15.5
Pennsylvania	15.5
Rhode Island	15.5
South Carolina	15.5
South Dakota	15.5
Tennessee	15.5
Texas	15.5
Utah	15.5
Vermont	15.5
Virginia	15.5
Washington	15.5
West Virginia	15.5
Wisconsin	15.5
Wyoming	15.5

Page 87 of 132

Term	Percentage
GMOs	95
Organic	95
Natural	95
Artificial	85
Organic	95
Natural	95
Artificial	85
Organic	95
Natural	95
Artificial	85
Organic	95
Natural	95
Artificial	85

[figure not shown]
Country	Percentage of population aged 65+ in 2010
Argentina	20.5%
Australia	21.5%
Austria	22.5%
Belgium	23.5%
Brazil	24.5%
Canada	25.5%
Chile	26.5%
Costa Rica	27.5%
France	28.5%
Germany	29.5%
Greece	30.5%
Hungary	31.5%
Italy	32.5%
Japan	33.5%
Mexico	34.5%
New Zealand	35.5%
Norway	36.5%
Portugal	37.5%
Switzerland	38.5%

[figure not shown]
Page 88 of 132

[figure not shown]
Confidential

Page 89 of 132

IBS Session Five

The entire block of text from approximately line 160 to line 738 is completely redacted with black bars.

[figure not shown]
IBS Session Six

[figure not shown]

The entire block of text from approximately line 774 to line 890 is completely redacted with black bars.

Page 93 of 132

Confidential

[figure not shown]
Page 96 of 132

[figure not shown]
IBS Session Seven

Page 97 of 132

Page 98 of 132

Page 99 of 132

A 10x10 grid of black bars on a white background. The bars are arranged in a pattern where they are either fully visible or completely hidden by other bars. The visible bars are located at the following coordinates: (1,1), (1,2), (1,3), (1,4), (1,5), (1,6), (1,7), (1,8), (1,9), (1,10), (2,1), (2,2), (2,3), (2,4), (2,5), (2,6), (2,7), (2,8), (2,9), (2,10), (3,1), (3,2), (3,3), (3,4), (3,5), (3,6), (3,7), (3,8), (3,9), (3,10), (4,1), (4,2), (4,3), (4,4), (4,5), (4,6), (4,7), (4,8), (4,9), (4,10), (5,1), (5,2), (5,3), (5,4), (5,5), (5,6), (5,7), (5,8), (5,9), (5,10), (6,1), (6,2), (6,3), (6,4), (6,5), (6,6), (6,7), (6,8), (6,9), (6,10), (7,1), (7,2), (7,3), (7,4), (7,5), (7,6), (7,7), (7,8), (7,9), (7,10), (8,1), (8,2), (8,3), (8,4), (8,5), (8,6), (8,7), (8,8), (8,9), (8,10), (9,1), (9,2), (9,3), (9,4), (9,5), (9,6), (9,7), (9,8), (9,9), (9,10), (10,1), (10,2), (10,3), (10,4), (10,5), (10,6), (10,7), (10,8), (10,9), (10,10).

APPENDIX C. GUT-DIRECTED HYPNOTHERAPY DAILY PRACTICE SESSION SCRIPT

Country	Percentage (%)
Angola	98
Argentina	98
Armenia	98
Aruba	98
Australia	98
Austria	98
Azerbaijan	98
Bahrain	98
Bangladesh	98
Barbados	98
Belarus	98
Belgium	98
Bolivia	98
Bosnia and Herzegovina	98
Bulgaria	98
Cambodia	98
Cameroon	98
Canada	98
Chad	98
Chile	98
China	98
Croatia	98
Cuba	98
Cyprus	98
Czech Republic	98
Djibouti	98
Egypt	98
El Salvador	98
Equatorial Guinea	98
Eritrea	98
Eswatini	98
Egypt	98
Finland	98
France	98
Germany	98
Greece	98
Guatemala	98
Honduras	98
Hungary	98
Iceland	98
Iraq	60
Ireland	98
Israel	98
Italy	98
Japan	98
Jordan	60
Kazakhstan	98
Kenya	98
Latvia	98
Lithuania	98
Luxembourg	98
Macedonia	98
Malta	98
Moldova	98
Morocco	98
Mozambique	98
Namibia	98
Nepal	98
Nicaragua	98
Niger	98
Nigeria	98
North Macedonia	98
Peru	98
Philippines	98
Poland	98
Portugal	98
Romania	98
Russia	98
Rwanda	98
Saint Lucia	98
Saint Vincent and the Grenadines	98
Saudi Arabia	98
Singapore	98
Slovakia	98
Slovenia	98
Solomon Islands	98
South Africa	98
South Korea	98
Spain	98
Sweden	98
Switzerland	98
Taiwan	98
Togo	98
Tunisia	98
Uganda	98
Ukraine	98
Uganda	98
United Kingdom	98
United States	98
Uruguay	98
Vanuatu	98
Venezuela	98
Yemen	98
Zambia	98

Page 101 of 132

Confidential

Page 102 of 132

APPENDIX D MUSCLE RELAXATION SCRIPTS

Session One

Country	Percentage (%)
Argentina	17.5
Australia	17.5
Austria	17.5
Belgium	17.5
Brazil	17.5
Canada	20.0
Chile	17.5
Costa Rica	17.5
Czech Republic	17.5
Denmark	17.5
France	17.5
Germany	20.0
Greece	17.5
Hungary	17.5
Italy	17.5
Japan	20.0
Mexico	17.5
Netherlands	20.0
Norway	17.5
Portugal	17.5
Spain	17.5
Sweden	20.0
Switzerland	17.5
Turkey	17.5
United Kingdom	17.5
United States	17.5

Page 104 of 132

Confidential

Page 106 of 132

Session Two

Term	Percentage
GMOs	~75%
Organic	~95%
Natural	~95%
Artificial	~75%
Organic	~95%
Natural	~95%
Artificial	~75%
Organic	~95%
Natural	~95%
Artificial	~75%

Topic	Percentage
Smart homes	95
Smart cities	95
Smart grids	95
Smart transportation	95
Smart agriculture	95
Smart manufacturing	95
Smart healthcare	95
Smart energy storage	95
Smart waste management	95
Smart water management	95
Smart buildings	95
Smart transportation	95
Smart agriculture	95
Smart manufacturing	95
Smart healthcare	95
Smart energy storage	95
Smart waste management	95
Smart water management	95
Smart buildings	95
The concept of a 'smart city'	60

[figure not shown]
Session Three

Page 111 of 132

Confidential

Page 112 of 132

Confidential

Session Four

[figure not shown]

Page 114 of 132

[figure not shown]
Country	Percentage (%)
Argentina	92
Australia	93
Austria	94
Belgium	94
Brazil	95
Chile	95
Costa Rica	95
France	95
Germany	95
Greece	95
Hungary	95
Italy	95
Japan	95
Mexico	95
New Zealand	95
Norway	95
Portugal	95
Spain	95
Switzerland	95

Session Five

Page 118 of 132

Confidential

Page 119 of 132

Confidential

Page 120 of 132

A horizontal bar chart illustrating the percentage of the population aged 65+ in 2010 across 20 countries. The y-axis lists the countries, and the x-axis represents the percentage of the population aged 65+, ranging from 0% to 30%.

[figure not shown]
Country	Percentage of population aged 65+ (2010)
Argentina	10%
Australia	22%
Austria	24%
Belgium	25%
Brazil	26%
Bulgaria	27%
Canada	28%
Chile	29%
Costa Rica	29%
Czech Republic	29%
Denmark	29%
France	29%
Germany	29%
Greece	29%
Hungary	29%
Italy	29%
Japan	29%
Mexico	29%
Netherlands	29%
Norway	29%
Portugal	29%
Spain	29%
Sweden	29%
Switzerland	29%
Turkey	29%
United Kingdom	29%
United States	29%

Session Six

This figure consists of a grid of horizontal black bars. The bars are of varying lengths, suggesting data values. The grid is composed of several rows and columns. Some rows are fully visible, while others are partially cut off at the top or bottom. The lengths of the bars within a single row are consistent, indicating a single data series across different categories. The overall pattern suggests a structured dataset with missing or incomplete data points.

[figure not shown]

Session Seven

Page 125 of 132

Confidential

Page 127 of 132

Confidential

Page 128 of 132

APPENDIX E. MUSCLE RELAXATION DAILY PRACTICE SESSION SCRIPT

APPENDIX F GDH INTRO SCRIPT

Implementation notes:

1. The intro video will be played before the first treatment (no option to opt out).
2. Starting with Session 2, intro video will be accessible from a button/link near the large video play button (opt-in to watch).
3. The intro video will also be accessible from the help section of the app.

Intro Script (sentences in italics indicate GDH-specific text):

Welcome and thank you for participating in this important clinical study. Your treatment session will begin after this two-minute introductory video. Your treatment program will consist of seven 30-minute sessions, with two weeks between each session. You will be sent an email reminder 24 hours and 1 hour before each of your sessions, and a text message reminder 5 minutes before each of your sessions. It is important to do your treatment session on the day that it is scheduled. If you do miss a session, you will be notified by email. If you know in advance that you can't make your scheduled session time, you may re-schedule it in your app. All treatment sessions must be completed within 3 days of the originally scheduled date.

On days you don't have a treatment session, a "practice" session will be available to you. A minimum of three practice sessions per week is recommended, but you may complete a practice session every day you don't have a treatment session. You can always access your treatment or practice sessions by logging into this app. To play your treatment or practice session, press the large arrow-button on your app. The button is designed to always play the correct treatment or practice session.

If you are interrupted for any reason during your session, it's best to start over from the beginning. To do this, you may press the "begin again" button at any time. You may restart each of your sessions up to three times. When you successfully complete a session, press the "complete session" button.

Relaxation can improve gut symptoms. That's why during your sessions, *it is important to be in a quiet place where you can sit comfortably and will not be disturbed*. Be sure to place your phone in "Do Not Disturb" mode. Choose a place you can adjust the lights so that they are not too bright, and a place with a good wifi or cellular network connection. If possible, loosen any restrictive clothing. We recommend using headphones, earbuds, or quality speakers. Never view or listen to your sessions in a car, even if it is not moving.

If after completing your session you still feel like you are not fully alert, it is ok to sit for another few minutes before getting up. Thank you again for participating in this study.

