	
being evaluated, and at the same time the metaMe staff and investigators will not have knowledge of group assignments (see Section 7.2.1). Subjects will complete treatment, per their group assignment and all subsequent data collection will be done without human intervention via the Curebase platform.
 
The Phase 2 treatment period will initiate within 7 days of the onboarding call. Phase 2 will be initiated with the first treatment session followed by 6 additional treatment sessions occurring every 2 weeks for a total of 7 sessions over 12 weeks. Subjects will receive prompts to complete a short practice sessions on the 5th, 8th, and 11th day between treatments. Practice sessions are recommended but not required.
 
Phase 3 begins immediately after completion of Phase 2 treatment period. Subjects will provide 4 weeks of post-treatment symptom data via the ePRO and the Curebase platform. Symptoms reported in this run-out period will be used to determine the primary outcome and responder definition and secondary outcomes.
 
Phase 4 begins immediately after completion of Phase 3. Subjects will complete two post-treatment assessment periods and provide daily symptom assessments and additional instances of outcomes surveys via the ePRO and the Curebase platform. The LTE 4-week assessment periods are weeks 35 through 38 and weeks 61 through 64.
 
Compliance with treatment and data entry will be facilitated by email and text message reminders and prompts. Each subject will be compensated for participation and data collection based on a pre-defined schedule with a maximal milestone determined compensation of \$525 (Section 5.5).
 
ePRO symptom data and outcomes surveys will be collected according to a pre-defined schedule (Table 1).

Objectives:	
Primary Objective
 
The primary objective of this study is to demonstrate that in adults with Irritable Bowel Syndrome (IBS), an all-digital Gut-Directed Hypnotherapy (GDH) treatment program (Regulora) is superior in reducing abdominal pain intensity relative to an all-digital modified Jacobsonian Muscle Relaxation (MR) treatment program.

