The comparator control group will listen to digital video/audio recordings of 7 guided muscle relaxation (MR) sessions of approximately equivalent length to the GDH sessions (see [Appendix D](#) for session scripts), as well as a daily practice session approximately equivalent in length to the GDH practice sessions (see [Appendix E](#) for script) (9). Guided MR was chosen as the comparator control treatment after consultation with the FDA because of (a) the ease with which it can be adapted to a digital format and support the creation of a comparator treatment and (b) credibility as a treatment for IBS albeit with limited demonstrated efficacy (9).

The GDH and MR treatment modules consist of seven ~30-minute digital video and audio recordings of a female therapist. The video component of the treatment sessions occurs at the beginning of the treatment session and is used to simulate the face-to-face interaction of the therapist encounter. The video component is short and typically lasts less than 5 minutes before the screen goes black and subjects are taken through the audio component of treatment. The digital production of the GDH and MR scripts was a verbatim reading. In the case of the GDH scripts the therapist reader provided hypnotherapy-appropriate speech patterns (inflection, pause, and tone). Once therapy is initiated, subjects receive all 7 treatment sessions, every other week for a total treatment period of 12 weeks. During the 13 days between treatment sessions, a short audio session referred to as a “practice session” is made available to subjects. There is a single practice session script for each of the two treatment arms lasting 15 minutes. Subjects receive text message and email reminders with a recommendation to complete a minimum of three practice sessions during the 13 days between treatments. Practice sessions are recommended but not required (see [Appendix C](#) and [Appendix E: Daily Practice Sessions](#)).

The metaMe treatment platform also tracks subject use and progress with treatment modules. For example, the exact time that a subject starts and stops a treatment or practice module is captured by the treatment platform. The software also tracks treatment sessions and only allows subjects to access treatments in sequence. The metaMe treatment platform on the EAGLEFISH app contains these major functional elements:

1. Treatment videos/audios
2. A secure cloud-based data repository.

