initiate treatment by pressing the large arrow start button on the home screen (see User Guide and [Figure 3](#)). The first thing subjects will see is a short 3-minute intro video that explains the following details of treatment:

1. Treatment session length
2. The treatment reminder system, which uses emails and text messages to alert subjects of upcoming treatment sessions and to remind subjects to complete treatment.
3. The process for rescheduling and managing missed treatment sessions (subjects have 3 additional days to complete the treatment before they are considered a missed treatment)
4. Rules on interrupted treatment sessions (subjects must start over from the beginning and have 3 opportunities to finish the treatment before they are considered a missed treatment)
5. The recommended minimum number of practice sessions is 3 over the 13 days between treatments.

There are two intro videos customized to each of the two treatments. They differ in the treatment-specific instructions; in the case of the GDH treatment, the video has specific instructions on how to manage re-alerting after hypnotherapy (see [Appendix F](#)). In the case of the MR treatment, subjects are given guidance on how to manage muscle-specific complaints (see [Appendix G](#)) After the completion of the treatment session, subjects will be instructed to click a button indicating they have completed the session. This button appears upon completion of 100% of the length of the treatment session. A session is also considered completed if greater than 95% of the video is played and no button is pressed by midnight of that day local time. Subjects who miss their scheduled treatment will have 3 additional days in which to complete the treatment. They will receive daily text and email reminders to complete treatment. If after 3 days the subject has not completed the treatment session they will be locked out of that treatment and it will be scored as a missed treatment session. Similarly, subjects will receive a one-time reminder about Practice sessions on the 5th, 8th, and 11th day after each treatment. Subjects will be allowed to access one practice session per day for as many non-treatment days as they like but they will only receive 3 reminders at the indicated days.

The subject experience with the EAGLEFISH app is illustrated in the User Guide and briefly in [Figure 3](#).

Figure 3 metaMe Treatment Visual Narrative**EAGLEFISH User Interface (UI)**

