APPENDIX G MUSCLE RELAXATION INTRO SCRIPT

Implementation notes:

1. The intro video will be played before the first treatment (no option to opt out).
2. Starting with Session 2, intro video will be accessible from a button/link near the large video play button (opt-in to watch).
3. The intro video will also be accessible from the help section of the app.

Welcome and thank you for participating in this important clinical trial. Your treatment session will begin after this 2-minute introductory video.

Your treatment program will consist of seven 30-minute sessions, with 2 weeks between each session. An email reminder will be sent to you 24 hours and 1 hour before each of your sessions. And a text message reminder will be sent to you 5 minutes before each of your sessions.

It's important to do your treatment session on the day that it's scheduled. If you miss a session, you'll be notified by email. If you know in advance that you cannot make a scheduled session, you may re-schedule it in this app. But all treatment sessions must be completed within 3 days of the originally scheduled date.

On days when you **don't** have a treatment session, a "practice" session will be available. A minimum of 3 practice sessions between treatment sessions is recommended. You may complete a practice session on any day that you don't have a treatment session.

You can always access your treatment or practice sessions by logging into this app. To play your treatment or practice session, press the large arrow button in the app. It will always play the correct treatment or practice session.

If you're interrupted during a session, it's best to start over from the beginning. To do this, press the "Begin Again" button at any time. You may restart each session up to 3 times.

When you successfully complete a session, press the "complete session" button.

Relaxation can improve gut symptoms. That's why it is important to find a comfortable position for your sessions, preferably lying in a recliner or on a bed. Be sure you're in a quiet place where you won't be disturbed. And put your phone in "Do Not Disturb" mode. If possible, loosen any tight or restrictive clothing. Choose a place where you can adjust the lights so they're not too bright, and someplace with a good Wi-Fi or cellular network connection. Place your smartphone

Page 132 of 132

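### The GDH intro script recommends three practice sessions per week, while Section 7.1.1 and the MR script recommend three per two-week interval

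*Combined protocol and SAP*

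**What the plan says.** The recommended minimum amount of practice is stated in four places.

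- **Appendix F (GDH introduction script):** "A minimum of three practice sessions per week is recommended".
- **Appendix G (MR introduction script):** "A minimum of 3 practice sessions between treatment sessions is recommended".
- **Section 7.1.1, on reminders, without distinction of arm:** "Subjects receive text message and email reminders with a recommendation to complete a minimum of three practice sessions during the 13 days between treatments".
- **Section 7.1.1, fifth item in the list of what the introduction video explains:** "The recommended minimum number of practice sessions is 3 over the 13 days between treatments".

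Reminder timing is also described. Section 7.1.1 says that "subjects will receive a one-time reminder about Practice sessions on the 5th, 8th, and 11th day after each treatment", and the Synopsis agrees: "Subjects will receive prompts to complete a short practice sessions on the 5th, 8th, and 11th day between treatments". Section 5.1 applies this schedule to GDH and MR alike.

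On the two introduction videos, Section 7.1.1 says "They differ in the treatment-specific instructions". It then names re-alerting after hypnosis for GDH and muscle complaints for MR. Section 5.2.1 says that the comparator will match GDH in the frequency of both treatments and practice. It adds that there is no evidence that practice changes outcome.

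**The concern.** Appendix F is the operative script for a video that every GDH subject must watch before the first session. Its practice minimum differs from the one Section 7.1.1 prescribes for that same video, and from the one in the MR script. A practice minimum is not among the treatment-specific differences that Section 7.1.1 names, so the discrepancy looks like a drafting slip and not a design choice.

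Two things are at stake. Between arms, the comparator is meant to match GDH in practice frequency, but the scripts recommend unequal amounts. Within the GDH arm, subjects would hear one minimum in the video and then receive reminders recommending about half of it. Section 7.3 counts completed practice sessions per subject as part of compliance. A difference between arms in those counts would be harder to interpret if the arms had been told different things.

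**Working it through.** No sample size, power or alpha figure depends on this point. The check is a comparison of texts with one conversion to a common unit.

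**Inputs**
- Section 7.1.1 and Appendix G: 3 practice sessions per interval between treatments.
- Appendix F: 3 practice sessions per week.
- Length of an interval: two weeks between sessions (Appendices F and G), of which 13 days lie between treatments (Section 7.1.1).

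**Plan's own figure.** Section 7.1.1 gives 3 per interval directly. Appendix G gives the same number, so these two sources agree without calculation.

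**Appendix F converted to an interval**
- Two full weeks: 3 × 2 = 6.
- The 13 days between treatments: 3 × 13/7 = 5.57.

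**Ratio of the GDH script to Section 7.1.1 and the MR script**
- Two-week basis: 6/3 = 2.00.
- 13-day basis: 5.57/3 = 1.86.

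**Converse check, in sessions per week.** Three per interval is 3/2 = 1.5 on the two-week basis, or 3 × 7/13 = 1.62 on the 13-day basis, against 3 in Appendix F. Neither way of counting the days reconciles the two statements.

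**Could the difference be intended?** The list in Section 7.1.1 describes the introduction video before the text separates the two versions, so its minimum applies to both. The differences it then names do not include practice. No other part of the protocol sets a weekly minimum for GDH.

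**After correction.** With the Appendix G sentence in Appendix F, the minimum is 3 per interval in both arms and the ratio is 3/3 = 1.

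**The case against.** The strongest reply is that little follows from the slip. Practice is recommended, not required. Both arms may practise once on any non-treatment day, and both get the same three reminders. The GDH video is compulsory only once, before the first session, while Section 7.1.1 has the reminders carrying the correct minimum in each interval. Section 5.2.1 speaks of frequency and states no minimum, so delivered scheduling does match even if the scripts do not. All of this stands and keeps the point minor. It does not reconcile Appendix F with Section 7.1.1, which specifies the content of that same video.

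Three stronger readings are tempting but unsupported.

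- **That GDH subjects will practise twice as much, favouring GDH on the primary endpoint.** The documents give only a scripted recommendation. They do not show what was recorded or how much subjects practised, and Section 5.2.1 reports no evidence that practice affects outcome.
- **That Appendix F's own formatting proves the sentence is common text.** The legend says "sentences in italics indicate GDH-specific text", and the practice sentence shows no italics in the text as extracted. But the closing re-alerting advice, which is plainly GDH-specific, shows none either. The formatting is not reliable evidence.
- **That reminders on days 5, 8 and 11 are a further stated minimum.** They are a count of prompts. They fit three per interval, but the recommendation itself is stated separately.

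**Conclusion.** The inconsistency is real and minor. Appendix F states a practice minimum 1.9 to 2.0 times that in Section 7.1.1 and Appendix G. It is more than a typographical matter, because following the script as written gives the experimental arm a higher recommendation than the control arm, contrary to Section 7.1.1 and to the matching intended in Section 5.2.1.

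The conclusion about what subjects hear assumes that the GDH video was recorded as scripted, which the documents do not show. The ratio describes the stated minimum only and assumes sessions on schedule. No effect on response rates, power or the primary test is claimed, and none can be derived from the documents.

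**What to change.** 1. Replace the Appendix F sentence with the Appendix G wording: "A minimum of 3 practice sessions between treatment sessions is recommended".
2. Check the deployed GDH video. If it already states three per interval, only the appendix needs correcting.
3. If it says three per week, correct that line. If randomisation has begun, record which version each subject saw, since GDH subjects will then have had different introductions.
4. Summarise completed practice sessions by arm, descriptively, if the SAP does not already do so. Section 7.3 already calculates the counts per subject, treatment adherence is already an exploratory endpoint (Section 4.2.3), and Section 9.4.4 leaves the detail of that analysis to the SAP.

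Leave the primary analysis and the sample size unchanged.

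The cost is one sentence, one check of a video, possibly one re-recorded line, and one table from data already collected. Section 1.4 requires IRB approval before a protocol amendment is implemented and sends subject materials to the IRB, so the text change and any new recording should go through that step.
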